6.2 Days to the best response

(1) Analysis set to be used

Patients included in efficacy evaluation who complete best response assessment analysis set

(2) Data to be analyzed

The frequency of days to the best response (1 to 21 days, 22 to 42 days, 43 to 63 days, [segmented similarly using a 21-day time window thereafter], 316 to 336 days, or ≥ 337 days) in patients with Hodgkin's lymphoma and patients with anaplastic large-cell lymphoma will be analyzed and summary statistics will be calculated. For the handling of best response assessment data, see Section 1.7.

Figure/table number

Table 6.2 and Figure 6.2

6.3 Overall survival

(3) Analysis sets to be used

Patients included in efficacy evaluation

(4) Data to be analyzed

The 1-year survivals with two-sided 95% confidence intervals in patients will be calculated using the Kaplan-Meier method, and a Kaplan-Meier plot will be generated for Hodgkin's lymphoma and patients with anaplastic large-cell lymphoma respectively.

(5) Figure/table number

Table 6.3 and Figure 6.3

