## 7.0 Methods

### 7.1 Observation period

From the start of treatment with Adcetris until the completion of 16 cycles [3 weeks per cycle]

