###### 2) When to collect outcome measure data

After 16 cycles of treatment with Adcetris (or upon discontinuation of treatment with Adcetris)

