Days from the date of the last dose of Adcetris to hematopoietic stem cell transplantation (homologous) (Post-baseline hematopoietic stem cell transplantation: homologous)	For patients with post-baseline hematopoietic stem cell transplantation (homologous), this data item will be calculated using the following formula: date of hematopoietic stem cell transplantation (homologous) – date of the last dose of Adcetris + 1. If the date of post-baseline hematopoietic stem cell transplantation (homologous) is missing, this data item should be handled as missing. For patients with no post-baseline hematopoietic stem cell transplantation (homologous), this data item should be handled as missing.
Duration of treatment with Adcetris prior to hematopoietic stem cell transplantation (homologous) (Post-baseline hematopoietic stem cell transplantation: stem cell transplantation: homologous)	For patients with post-baseline hematopoietic stem cell transplantation (homologous), this data item will be calculated using the following formula: date of the last dose of Adcetris – date of the initial dose of Adcetris + 1. If the date of post-baseline hematopoietic stem cell transplantation (homologous) is missing, this data item should be handled as missing.

Term	Definition
homologous)	For patients with no post-baseline hematopoietic stem cell transplantation (homologous), this data item should be handled as missing.
Date of the final observation	“Date of the final observation” in the case report form If not provided, the most recent date entered in the case report form should be used.
Summary statistics	Number of patients, mean, standard deviation, minimum, 25th percentile, median, 75th percentile, and maximum.
Overall survival	Time to the date of death from any cause after the date of the initial dose of Adcetris. Surviving patients will be censored on the date of survival confirmation. The date of outcome of an adverse event with “Died/fetal” recorded in the Outcome field will be used as the date of death, and the final observation date will be used as the date of survival confirmation. The overall survival (date of death or survival confirmation) = date of death or survival confirmation – date of the initial dose of Adcetris+1
1 year	One year is defined as 365.25 days.
1 month	One month is defined as 30.4375 days.

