After 11 cycles	
 • If Cycle 12 is initiated: Date of Cycle 12 • If Cycle 12 is not initiated: 21 days after the date of Cycle 11 	
 • If Cycle 12 is initiated: From the day after the date of Cycle 11 to the day of Cycle 12 • If Cycle 12 is not initiated: From the day after the date of Cycle 11 to 21 days after the date of Cycle 11
After 12 cycles	
 • If Cycle 13 is initiated: Date of Cycle 13 • If Cycle 13 is not initiated: 21 days after the date of Cycle 12 	
 • If Cycle 13 is initiated: From the day after the date of Cycle 12 to the day of Cycle 13 • If Cycle 13 is not initiated: From the day after the date of Cycle 12 to 21 days after the date of Cycle 12
After 13 cycles	
 • If Cycle 14 is initiated: Date of Cycle 14 • If Cycle 14 is not initiated: 21 days after the date of Cycle 13 	
 • If Cycle 14 is initiated: From the day after the date of Cycle 13 to the day of Cycle 14 • If Cycle 14 is not initiated: From the day after the date of Cycle 13 to 21 days after the date of Cycle 13

Time point for testing	Date of protocol-specified assessment	Acceptable time window
After 14 cycles	
 • If Cycle 15 is initiated: Date of Cycle 15 • If Cycle 15 is not initiated: 21 days after the date of Cycle 14 	
 • If Cycle 15 is initiated: From the day after the date of Cycle 14 to the day of Cycle 15 • If Cycle 15 is not initiated: From the day after the date of Cycle 14 to 21 days after the date of Cycle 14
After 15 cycles	
 • If Cycle 16 is initiated: Date of Cycle 16 • If Cycle 16 is not initiated: 21 days after the date of Cycle 15 	
 • If Cycle 16 is initiated: From the day after the date of Cycle 15 to the day of Cycle 16 • If Cycle 16 is not initiated: From the day after the date of Cycle 15 to 21 days after the date of Cycle 15

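### SAP 6.3 asks for 1-year survival by disease group, but scheduled observation of a survivor ends at about day 337 or at discontinuation

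*SAP*

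**What the plan says.** SAP 6.3 specifies, in the efficacy population and separately for Hodgkin's lymphoma and anaplastic large-cell lymphoma: "The 1-year survivals with two-sided 95% confidence intervals in patients will be calculated using the Kaplan-Meier method", together with a Kaplan-Meier plot. The definitions table in SAP 1.0 fixes the landmark ("One year is defined as 365.25 days") and the censoring rule for survivors ("the final observation date will be used as the date of survival confirmation"). Protocol 10.5.2 uses the same censoring date. If the final observation date is blank, the SAP adds a fallback: "If not provided, the most recent date entered in the case report form should be used".

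Protocol 7.1 defines the observation period: "From the start of treatment with Adcetris until the completion of 16 cycles [3 weeks per cycle". Protocol 9.2.4.3 gives the collection time of the final observation date: "After 16 cycles of treatment with Adcetris (or upon discontinuation of treatment with Adcetris". The schedule in Protocol Appendix 1 marks that item only in the columns for the end of 16 cycles and for discontinuation, and has no later column.

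Protocol 10.5.2 asks for time to death from any cause. It does not ask for a 1-year figure.

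**The concern.** The landmark lies beyond the point at which the plan stops looking at a surviving patient who keeps to schedule. A Kaplan-Meier estimate at 365.25 days draws its information about the last weeks only from patients still at risk then. If those patients got there through treatment delay, longer treatment or an unresolved adverse event, they may differ from the rest.

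If nobody in a disease group remains at risk, SAP 6.3 does not say whether the value is reported as not estimable or the last earlier estimate is carried forward with its interval. It also does not ask for numbers at risk. A table could then carry a 1-year label and a 95% interval that follow-up does not support.

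**Working it through.** **Inputs**
- Landmark: 365.25 days (SAP 1.0 definitions).
- Survival time: date of death or censoring minus first-dose date, plus 1, so the first dose is day 1 (SAP 1.0 definitions).
- Observation: 16 cycles of 21 days (Protocol 7.1).
- One month: 30.4375 days (SAP 1.0 definitions).
- Estimated enrollment: 140 (Protocol 3.1).

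**1. The plan's own figure.** Section 1.4 of a superseded SAP version placed the after-16-cycles time point at first dose + 336 days. 16 × 21 = 336, so it reproduces. On the survival scale this is 336 + 1 = day 337.

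**2. Shortfall for an on-schedule completer.** 365.25 − 337 = 28.25 days; 337 / 365.25 = 0.923 year.

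**3. Early stoppers.** If observed to the end of their last cycle, patients stopping after k cycles are censored at day 21k + 1:

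| Cycles | Censoring day | Short of 365.25 by |
|---|---|---|
| 4 | 85 | 280.25 |
| 8 | 169 | 196.25 |
| 12 | 253 | 112.25 |

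**4. What it takes to be at risk at 365.25 days.** In whole days, survival time must be at least 366.
- *Dose delay.* A completer needs 366 − 337 = 29 days in total, or 29 / 15 = 1.9 days per interval between doses.
- *More cycles* (SAP 4.1 has a category for 17 or more). If observation is carried on, the end of Cycle 17 is 17 × 21 + 1 = day 358, still 7.25 days short; the end of Cycle 18 is day 379.
- *A late final observation date.* Protocol 7.4 allows one month after Cycle 16 to complete the form. With no delay this runs to 337 + 30 = day 367, so only days 366 and 367 would qualify. With one 7-day delay it runs to 344 + 30 = day 374.
- *Adverse-event follow-up after stopping* (Protocol 7.4), which has no fixed length.
- *The fallback to the latest date in the form.*

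These routes can combine. None is a survival contact planned for all patients.

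**5. How many might get there.** The documents give no delay or completion rates, so the following rests on assumptions. Suppose each of the 15 later doses is delayed 7 days with probability q, nobody dies, and observation ends 21 days after the last dose. A completer then needs at least 5 delays (5 × 7 = 35, which is at least 29). If all 140 complete, the expected number at risk is 140 × P(Binomial(15, q) ≥ 5). A simulation under the same assumptions, with a 10% chance of stopping per cycle (0.9^15 = 0.206 complete 16 cycles), gives the last column.

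| q | All complete | 10% stop per cycle |
|---|---|---|
| 0 | 0 | 0 |
| 0.1 | 1.8 | 0.4 |
| 0.2 | 23 | 4.8 |
| 0.3 | 68 | 14 |
| 0.5 | 132 | 28 |

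These counts come before the split into two disease groups. The range runs from nobody to nearly everybody, so the number at risk cannot be predicted from the plan.

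**The case against.** The strongest reply is that observation is defined by cycles, not days, and that the plan expects cycles to stretch. SAP 1.4 ties laboratory windows to actual cycle dates, the dose per 3 weeks is computed from actual dates, and treatment interruption or delay is an analysis category in SAP 5.9. Under 2 days of delay per interval takes a completer past the landmark, and the routes add up. This stands: the documents show that 1-year follow-up is not secured, not that it will be thin.

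It also rules out four stronger readings that a reader might infer.
- *Nobody can be at risk at 1 year.* That holds only with exact 21-day cycles and no added observation.
- *Completers are censored at the 16th dose, day 15 × 21 + 1 = 316.* The final SAP's laboratory time points do stop there, but they say nothing about the final observation date, and the 16th dose follows 15 cycles, not 16.
- *There is a latest possible censoring day for early stoppers.* Their form deadline in Protocol 7.4 runs from completion of required observation, whose length is not given, and adverse-event follow-up is open-ended.
- *The 1-year figure should be dropped outright.* With the number at risk unknown, that goes too far.

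It can also be said that Kaplan-Meier handles censoring and that the required plot shows where each curve ends. The first is true only while patients remain at risk and censoring is non-informative. The second helps, but an endpoint on a plot gives neither the number at risk nor a rule for the tabulated value.

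**Conclusion.** The point holds as a mismatch between the landmark and scheduled follow-up. A completer on exact 21-day cycles, observed to the end of Cycle 16, is censored 28.25 days before 365.25 days; early stoppers are normally censored sooner; and no section plans vital status at 1 year for all patients. The 1-year estimate would rest on patients who passed day 365 by unplanned routes, or be not estimable in a disease group.

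Censoring may also be informative. The discontinuation reasons in SAP 4.1 include adverse events and inadequate response, and adverse-event collection, the source of death dates, normally ends at 16 cycles or discontinuation. A reader might infer that survival will be overstated, but the documents do not fix a direction.

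The consequence is limited. Protocol 2.0 collects efficacy for reference and SAP 6.3 tests no hypothesis. What is at stake is the label and interval in Table 6.3 and Figure 6.3.

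**What to change.** In SAP 6.3:
1. Make the main survival figure an estimate at a fixed time inside scheduled observation, for example day 336, set without reference to deaths and labelled as survival during the observation period.
2. Show numbers at risk on each disease-specific curve and at every reported time point.
3. Report the 1-year estimate and interval only for a disease group with patients still at risk at 365.25 days. Otherwise state that it is not estimable, and do not carry the last estimate forward.
4. State as a limitation that survival follow-up is not planned beyond 16 cycles or discontinuation, so later deaths are not systematically captured and censoring may be informative in an unknown direction.

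The cost is SAP wording, labels and a numbers-at-risk row. No new data are needed, and Protocol 10.5.2 needs no change. The downside is that the 1-year figure may be lost or shown as not estimable. Moving the main time point does not remove any informative censoring, which is why item 4 is needed. A 1-year figure supported by design would need vital status to day 366 for all patients, which is not planned.

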Appendix: Definition of Pulmonary Disorders (MedDRA Preferred Terms)

• Acute interstitial pneumonitis (10066728)	• Idiopathic pneumonia syndrome (10063725)	• Pulmonary haemosiderosis (10037396)
• Acute lung injury (10069351)	• Idiopathic pulmonary fibrosis (10021240)	• Pulmonary necrosis (10058824)
• Acute respiratory distress syndrome (10001052)	• Interstitial lung disease (10022611)	• Pulmonary oedema (10037423)
• Acute respiratory failure (10001053)	• Lung disorder (10025082)	• Pulmonary radiation injury (10061473)
• Alveolar proteinosis (10001881)	• Lung infiltration (10025102)	• Pulmonary sarcoidosis (10037430)
• Alveolitis (10001889)	• Necrotising bronchiolitis (10070831)	• Pulmonary toxicity (10061924)
• Alveolitis allergic (10001890)	• Obliterative bronchiolitis (10029888)	• Pulmonary vasculitis (10037457)
• Systemic sclerosis pulmonary (10042954)	• Organising pneumonia (10067472)	• Radiation alveolitis (10037754)
• Alveolitis necrotising (10050343)	• Pneumonitis (10035742)	• Radiation fibrosis – lung (10037758)
• Bronchiolitis (10006448)	• Pneumonitis chemical (10035745)	• Radiation pneumonitis (10037765)
• Diffuse alveolar damage (10060902)	• Progressive massive fibrosis (10036805)	• Respiratory arrest (10038669)
• Eosinophilic pneumonia (10014962)	• Pulmonary alveolar haemorrhage (10037313)	• Respiratory distress (10038687)
• Eosinophilic pneumonia acute (10052832)	• Pulmonary eosinophilia (10037382)	• Respiratory failure (10038695)
• Eosinophilic pneumonia chronic (10052833)	• Pulmonary fibrosis (10037383)	• Sarcoidosis (10039486)
• Hypoxia (10021143)	• Pulmonary granuloma (10037391)	

The above definition is consistent with the one used in clinical studies of Adcetris.

Statistical Analysis Plan

ADCETRIS IV Infusion – Special Drug Use Surveillance (All-case Surveillance) "Relapsed or Refractory CD30+ Hodgkin's Lymphoma or Anaplastic Large Cell Lymphoma"

PPD

Takeda Pharmaceutical Company Limited

PPD

Statistical Analysis Agent

PPD

[figure not shown]

Table of Contents

1.0	Definition of Terms and Handling of Test/Measurement Data	1
1.1	Definition	1
1.2	Display digits	8
1.3	Level of significance	8
1.4	Handling of test data	8
2.0	Patient Disposition (Patient Disposition Diagram)	10
3.0	Patient Demographics and Baseline Characteristics	11
4.0	Treatment Given	14
4.1	Treatment given	14
4.2	Premedication to prevent infusion reaction	15
5.0	Safety Analysis	16
5.1	Occurrences of adverse events/infections and adverse drug reactions/infections	16

1.0 Definition of Terms and Handling of Test/Measurement Data

1.1 Definition

Term	Definition
This/the product	Refers to Adcetris for intravenous drip infusion in this Statistical Analysis Plan.
SOC	MedDRA/J System Organ Class
HLGT	MedDRA/J High Level Group Term
PT	MedDRA/J Preferred Term
LLT	MedDRA/J Lowest Level Term
Patients registered	Patients whose registration has been approved
Patients whose case report forms are available	Patients whose case report forms have been collected
Patients whose case report forms are not available	Patients registered but whose case report form have not been collected
Fixed patients	Patients whose case report forms are available, with the date of case report form completion entered in the PMS system
Non-fixed patients	Patients whose case report forms are available, with the date of case report form completion not entered in the PMS system
Safety analysis set	Fixed patients included in the safety analysis set
Safety analysis set (Hodgkin's lymphoma)	Patients included in the safety analysis set whose diagnosis is Hodgkin's lymphoma
Safety analysis set (anaplastic large-cell lymphoma)	Patients included in the safety analysis set whose diagnosis is anaplastic large-cell lymphoma
Patients excluded from the safety analysis set	Fixed patients excluded from the safety analysis set
Efficacy analysis set	Patients included in the safety analysis set who are also included in the efficacy analysis set
Patients excluded from the efficacy analysis set	Patients included in the safety analysis set who are excluded from the efficacy analysis set
Patients completing treatment	Patients completing 16 cycles of treatment with Adcetris
Patients discontinuing treatment	Patients not completing 16 cycles of treatment with Adcetris
Adverse events, etc.	Refers to "adverse events and infections." In this Statistical Analysis Plan, the term "adverse events and infections" is used in titles and the term "adverse events, etc." is used in text and tables.
Adverse drug reactions, etc.	Refers to "adverse drug reactions and infections." Adverse events, etc., not considered "not related" to Adcetris by the investigator.

Term	Definition
	In this Statistical Analysis Plan, the term “adverse drug reactions and infections” is used in titles and the term “adverse drug reactions, etc.” is used in text and tables.
Serious adverse events, etc.	Refers to “serious adverse events and infections.” Adverse events considered “serious” by the investigator. Events listed in the MedDRA Coding List in the Takeda Medically Significant AE List should be regarded as serious even if they are considered “non-serious” by the investigator. In this Statistical Analysis Plan, the term “serious adverse events and infections” is used in titles and the term “serious adverse events, etc.” is used in text and tables.
Number of patients with adverse events/adverse drug reactions	Number of patients experiencing adverse events, etc., or adverse drug reactions, etc.
Number of adverse events/adverse drug reactions	Number of adverse events, etc., or adverse drug reactions, etc., observed
Percentage of patients with adverse events/adverse drug reactions	[For safety analysis using patients included in the safety analysis set] Is calculated using the following formula: (number of patients with adverse events/adverse drug reactions) / (number of patients included in the safety analysis set) × 100. [For safety analysis using patients excluded from the safety analysis set] Is calculated using the following formula: (number of patients with adverse events/adverse drug reactions) / (number of patients excluded from the safety analysis set) × 100.
Percentage of adverse events/adverse drug reactions observed	[For safety analysis using patients included in the safety analysis set] Is calculated using the following formula: (number of adverse events/adverse drug reactions observed) / (number of patients included in the safety analysis set) × 100. [For safety analysis using patients excluded from the safety analysis set] Is calculated using the following formula: (number of adverse events/adverse drug reactions observed) / (number of patients excluded from the safety analysis set) × 100.
Time of onset	Is calculated using the following formula: date of onset of adverse events, etc. (or adverse drug reactions, etc.) – date of the initial dose of Adcetris + 1. If the day and month of onset of adverse events, etc. (or adverse drug reactions, etc.) are unknown, the date of onset should be “January 1.” However, if the year of the initial dose of Adcetris is the year of onset of adverse events, etc. (or adverse drug reactions, etc.), the date of onset

Term	Definition																									
	
should be the day and month of the initial dose of Adcetris.
 
If the day of onset of adverse events, etc. (or adverse drug reactions, etc.) is unknown, the date of onset should be the first day of the month.
 
However, if the year and month of the initial dose of Adcetris is the year and month of onset of adverse events, etc. (or adverse drug reactions, etc.), the date of the initial dose of Adcetris should be the date of onset.
																									
Patients with concurrent hepatic disorder	Patients having a concurrent illness that falls under the category of Standardized MedDRA Query (SMQ) Code 20000005 (SMQ Hepatic disorders [Scope: Narrow])																									
Grade of hepatic disorder	
The ALT or AST level at baseline with the highest CTCAE grade will be used to determine the grade of hepatic disorder. The grades of ALT and AST levels will be determined according to the following tables:
 
  
 ALT	Male	Female	
   
 None	≤42 IU/L	≤23 IU/L	
 
 Grade 1	>42 to 126 IU/L	>23 to 69 IU/L	
 
 Grade 2	>126 to 210 IU/L	>69 to 115 IU/L	
 
 ≥Grade 3	>210 IU/L	>115 IU/L	
  
 
  
 AST		
   
 None	≤30 IU/L	
 
 Grade 1	>30 to 90 IU/L	
 
 Grade 2	>90 to 150 IU/L	
 
 ≥Grade 3	>150 IU/L	
  
	ALT	Male	Female	None	≤42 IU/L	≤23 IU/L	Grade 1	>42 to 126 IU/L	>23 to 69 IU/L	Grade 2	>126 to 210 IU/L	>69 to 115 IU/L	≥Grade 3	>210 IU/L	>115 IU/L	AST		None	≤30 IU/L	Grade 1	>30 to 90 IU/L	Grade 2	>90 to 150 IU/L	≥Grade 3	>150 IU/L
ALT	Male	Female																								
None	≤42 IU/L	≤23 IU/L																								
Grade 1	>42 to 126 IU/L	>23 to 69 IU/L																								
Grade 2	>126 to 210 IU/L	>69 to 115 IU/L																								
≥Grade 3	>210 IU/L	>115 IU/L																								
AST																										
None	≤30 IU/L																									
Grade 1	>30 to 90 IU/L																									
Grade 2	>90 to 150 IU/L																									
≥Grade 3	>150 IU/L																									
Patients with concurrent renal disorder	Patients having a concurrent illness that falls under the category of Takeda MedDRA Query (TMQ) (Renal disease)																									
Grade of renal disorder: None	
The serum creatinine level at baseline is:
 
≤1.07 mg/dL for males
 
≤0.79 mg/dL for females
																									
Grade of renal disorder: 1	
The serum creatinine level at baseline is:
 
>1.07 to 1.605 mg/dL for males
 
>0.79 to 1.185 mg/dL for females
																									
Grade of renal disorder: 2	
The serum creatinine level at baseline is:
 
>1.605 to 3.21 mg/dL for males
 
>1.185 to 2.37 mg/dL for females
																									
Grade of renal disorder: ≥3	
The serum creatinine level at baseline is:
 
>3.21 mg/dL for males
 
>2.37 mg/dL for females
																									
Patients with a past history of	Patients with a past history that falls under the category of Appendix																									

Term	Definition
pulmonary disorder	“Definition of Pulmonary Disorders” (If “No concurrent illness existed at the initiation of treatment with Adcetris” is selected in the field of “Past history/concurrent illness of pulmonary disorders” in the case report form, the pulmonary disorder should be regarded as a past history.)
Patients with concurrent pulmonary disorder	Patients with a concurrent illness that falls under the category of Appendix “Definition of Pulmonary Disorders” (If “A concurrent illness existed at the initiation of treatment with Adcetris” is selected in the field of “Past history/concurrent illness of pulmonary disorders” in the case report form, the pulmonary disorder should be regarded as a concurrent illness.)
Patients with a past history of malignant tumour	Patients with a past history that falls under the category of MedDRA SMQ Code 20000194 (SMQ Malignant tumours [Scope: Narrow]) (If “No concurrent illness existed at the initiation of treatment with Adcetris” is selected in the field of “Past history/concurrent illness of malignant tumours” in the case report form, the pulmonary disorder should be regarded as a past history.)
Patients with concurrent malignant tumour	Patients with a concurrent illness that falls under the category of MedDRA SMQ Code 20000194 (SMQ Malignant tumours [Scope: Narrow]) (If “A concurrent illness existed at the initiation of treatment with Adcetris” is selected in the field of “Past history/concurrent illness of malignant tumours” in the case report form, the pulmonary disorder should be as a concurrent illness.)
Patients with concurrent diabetes mellitus	Patients with a concurrent illness that falls under the category of MedDRA SMQ Code 20000041 (SMQ Hyperglycaemia/new onset diabetes mellitus [Scope: Narrow])
Patients with hypertension	Patients with a concurrent illness that falls under the category of MedDRA SMQ Code 20000147 (SMQ Hypertension [Scope: Narrow])
Patients with concurrent dyslipidaemia	Patients with a concurrent illness that falls under the category of MedDRA SMQ Code 20000026 (SMQ Dyslipidaemia [Scope: Narrow])
Patients with concurrent hyperuricaemia	Patients with a concurrent illness that falls under the category of MedDRA PT Code 10020903 (Hyperuricaemia)
Patients with concurrent infection	Patients with a concurrent illness that falls under the category of MedDRA SOC Code 10021881 (Infections and infestations)
Patients with concurrent peripheral neuropathy	Patients with a concurrent illness that falls under the category of SMQ Code 20000034 (SMQ Peripheral neuropathy [Scope: Narrow])
Patients with other concurrent illnesses	Patients with any concurrent illness other than those listed above
Antibiotics/synthetic	Prophylactics against infections that fall under the category of those with

Term	Definition
antibacterial agents	the first three digits of YJ Code being 611 to 616 or 619 (If more than one antibiotics/synthetic antibacterial agents are used in the same patient, it will be counted as one patient.)
Antifungals	Prophylactics against infections that fall under the category of those with the first three digits of YJ Code being 617 (If more than one antifungals are used in the same patient, it will be counted as one patient.)
Antivirals	Prophylactics against infections that fall under the category of those with the first three digits of YJ Code being 625 (If more than one antivirals are used in the same patient, it will be counted as one patient.)
Trimethoprim-sulfamethoxazole combinations	Prophylactics against infections that fall under the category of those with YJ Code being 629010007 to 9
Other prophylactics against infections	Any drug entered in the field of “Drugs used for the prevention of infection” other than prophylactics against infections listed above (If more than one other prophylactics against infections are used in the same patient, it will be counted as one patient.)
Peripheral sensory neuropathy (as an adverse event)	Adverse events with “Sensory neuropathy” entered in the “Category of peripheral nerve disorders” in the field of “Adverse events: [1] Peripheral nerve disorders] in the case report form. MedDRA PT Code 10034620 should be assigned regardless of data entered in “Symptoms” in the field.
Peripheral motor neuropathy (as an adverse event)	Adverse events with “Motor neuropathy” entered in the “Category of peripheral nerve disorders” in the field of “Adverse events: [1] Peripheral nerve disorders] in the case report form. MedDRA PT Code 10034580 should be assigned regardless of data entered in “Symptoms” in the field.
Peripheral neuropathy (as an adverse event)	Adverse events with “Other” entered in the “Category of peripheral nerve disorders” in the field of “Adverse events: [1] Peripheral nerve disorders] in the case report form. MedDRA PT Code 10029331 should be assigned, regardless of data entered in “Symptoms” in the field.
Pulmonary disorders (as adverse events)	Adverse events that fall under the category of Appendix “Definition of Pulmonary Disorders”
Infusion reaction	Adverse events entered in the field of “Adverse events: [4] Infusion reaction,” regardless of data entered in “Symptoms” in the field.
Patients with the onset of infection	Patients with adverse drug reactions that fall under the category of MedDRA SOC Code 10021881 (Infections and infestations)
Patients with the onset of bacterial infection	Patients with adverse drug reactions that fall under the category of MedDRA HGLT Code 10004018 (Bacterial infection), 10008555 (Chlamydial infection), 10028474 (Mycoplasma infection) or 10039135 (Rickettsia infection)
Patients with the onset of fungal infection	Patients with adverse drug reactions that fall under the category of MedDRA HGLT Code 10017528 (Fungal infection)

Term	Definition
Patients with the onset of viral infection	Patients with adverse drug reactions that fall under the category of MedDRA HGLT Code 10047438 (Viral infection)
Age	
If the month and day of the initial dose of Adcetris is < the month and day of birth, the patient's age will be calculated using the following formula: Year of the initial dose of Adcetris – year of birth – 1.
 
If the month and day of the initial dose of Adcetris is ≥ the month and day of birth, the patient's age will be calculated using the following formula: Year of the initial dose of Adcetris – year of birth.
 
If the month and day of birth are unknown, they should be “January 1,” and if the day of birth is unknown, it should be the first day of the month.

BMI	BMI should be calculated using the following formula: Weight (kg)/(0.0001 × height (cm) × height (cm)). The obtained value should be rounded off to one decimal place.
Disease duration	
The disease duration should be calculated using the following formula: [“Date of the initial dose of Adcetris” – “date of diagnosis of Hodgkin's or anaplastic large-cell lymphoma” +1]/365.25.
 
The day of diagnosis should be the first day of the month provided. If the month of diagnosis is unknown, the date of diagnosis should be “January 1st” of the year provided.

Mean dose of Adcetris	Is calculated as the total value of each dose of Adcetris given at each treatment cycle divided by the number of cycles.
Dose of Adcetris per 3 weeks	
Is calculated using the following formula: Total “dose of Adcetris”/([“date of the last dose of Adcetris” – “date of the initial dose of Adcetris” + 21)/21].
 
If only 1 cycle of treatment is given, the “date of the last dose of Adcetris” and the “date of the initial dose of Adcetris” should be regarded as the same.

Degree of decreased neutrophil count at baseline: No decrease	Neutrophil count at baseline $\geq 2,000 /\text{mm}^3$
Degree of decreased neutrophil count at baseline: Grade 1	Neutrophil count at baseline $< 2,000$ to $1,500 /\text{mm}^3$
Degree of decreased neutrophil count at baseline: Grade 2	Neutrophil count at baseline $< 1,500$ to $1,000 /\text{mm}^3$
Degree of decreased neutrophil count at baseline: Grade 3	Neutrophil count at baseline $< 1,000$ to $500 /\text{mm}^3$
Degree of decreased neutrophil count at baseline: Grade 4	Neutrophil count at baseline $< 500 /\text{mm}^3$
Date of the final observation	
“Date of the final observation” in the case report form
 
If not provided, the most recent date entered in the case report form should

Term	Definition
	be used.
Summary statistics	Includes mean, standard deviation, minimum, 25th percentile, median, 75th percentile, and maximum.

